8.6 Compliance

Patients will be asked to return their blister card(s) at each post-randomization study visit (except Day 1).

9 ADVERSE EVENTS

An adverse event can be any unfavorable or unintended sign (including a clinically significant abnormal laboratory finding), symptom, or disease temporally associated with the use of a medicinal (investigational) drug, whether or not it is related to the medicinal (investigational) drug.

9.1 Documenting Adverse Events

The recording of AEs (regardless of their relationship to study drug) will begin with the Screening Visit until the Final Visit (Day 56) or Early Termination Visit. If the Investigator is made aware of an AE up to 7 days after the last dose of study drug the AE will be followed to resolution. For those patients who enter the optional active treatment extension, Investigator(s) will query patients for AEs when they visit the site to pick up their medication every 8 weeks. Investigator(s) will monitor each patient closely for AEs. At each visit, the Investigator will document all observed or volunteered AEs.

The Investigator(s) should always attempt to group signs and symptoms into a single term that constitutes a single unifying diagnosis. Adverse Events will be classified using the latest version of the Medical Dictionary for Regulatory Activities (MedDRA) classification system. AEs reported from the first dose of IP until 7 days after the last dose of IP will be considered as treatment-emergent AEs (TEAEs) and will be summarized descriptively. The Investigator's opinion of the association of each AE to study drug, the duration (date of onset / date of resolution), frequency, intensity, countermeasures (treatment), and the outcome of each AE will be documented. Each adverse event must be recorded separately. Multiple occurrences of a single PT in a patient will only be counted once at the maximum severity/grade. All AEs will be summarized by relatedness to IP. Any AEs leading to death or discontinuation of IP will also be summarized.

Any medical condition or laboratory abnormality that is present at subject screening and prior to the first dose of study drug should be considered as baseline, recorded in medical history, and should not be reported as an AE. However, if the medical condition worsens at any time during the study after the first dose of study drug it should be recorded as an adverse event.

9.2 Assessment of Intensity and Causality

The event's **relationship to the study drug or treatment procedure** should be indicated according to the following definitions:

Definite	The adverse event is clearly related to the treatment or procedure.	
Possible	The adverse event may be related to the treatment or procedure.	
Unlikely	The adverse event is doubtfully related to the treatment or procedure.	
Not Related	The adverse event is clearly not related to the treatment or procedure.	

The **frequency** of the event should be indicated according to the following definitions:

Single episode	This is the first and only experience/episode of the event in the trial.
Recurrent	The event has occurred before in the trial.
Continuous	The event is continuing.

The **intensity** grade of the event should be indicated according to the following definitions:

Mild	The event is easily tolerated by the subject and does not affect the patient's usual daily activities.
Moderate	The event causes the subject sufficient discomfort and interferes with the patient's usual daily activities.
Severe	The event is incapacitating and causes considerable interference with the subject's usual daily activities.

Action Taken should be indicated according to the following definitions:

None	No treatment was required and no changes were made to study drug administration and dose.
Treatment	Subject received treatment, e.g., medications or procedures as a result of the AE.
Discontinued from Study	Subject was discontinued from study.
Discontinued study drug	Study drug was discontinued and not restarted.
Study drug interrupted	Dosing was stopped or delayed due to the AE.
Other	Specify

The **outcome** should be indicated according to the following definitions:

Recovered without sequelae	Patient recovered completely from the AE.
Recovered with sequelae	Patient has recovered from the AE but displays other symptoms.
Ongoing	Patient continues to exhibit symptoms of the AE. The patient will be followed until the AE is resolved.
Death	Patient died. (The date of death should be entered as the SAE resolution date)
Unknown	Outcome is unknown due to loss to follow-up.

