7.14 Flexible Sigmoidoscopy

To prepare for flexible sigmoidoscopy, recommendations will be given to patients the day before the scheduled sigmoidoscopy at Screening (within 2 weeks of the Screening visit) and for the Day 56 site visit (within 2 days of visit). The same instructions will be

given to patients prior to the Day 336 site visit (within 2 days of visit), for those participating in the active treatment extension. The recommendations may include:

- Follow a special diet the day before the exam. Patients may be asked to not eat the day before the exam. Drinks may be limited to clear liquids plain water, broth, carbonated beverages, and tea and coffee without milk or cream. Patients may be asked not to eat or drink anything after midnight the night before the exam.
- Take a laxative the night before the exam.
- Use an enema kit. Patients will need to use an over-the-counter enema kit, typically a few hours before the exam to empty their colon.

During the exam, patients may be sedated. The sigmoidoscopy will be recorded and scored by a blinded central reader. There is a high degree of correlation in assessments of UC activity made by rectosigmoidoscopy vs. colonoscopy (Colombel et al., 2016).

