9.8 Reporting Serious Adverse Events

The recording of SAEs (regardless of their relationship to study drug) will begin with the Screening visit until the Final Visit (Day 56 or 336 (if entering the extension) or Early Termination Visit. Any SAE, including death due to any cause, which occurs during the conduct of this study, regardless of relationship to study drug, must be reported within 24 hours of the Investigator's (or designee's) first awareness of the event.

An initial Serious Adverse Event Form (SAE form) should be completed and submitted through the CRF (or paper form as a backup) per the SAE form instructions.

The Investigators should attempt to group signs and symptoms into a single term that constitutes a single unifying diagnosis and indicated the serious criteria that are applicable to the SAE (the list of serious criteria is also provided in the above section. The Investigator's opinion of the relationship of the SAE to study drug, the duration, intensity, frequency, actions taken with study drug, and the outcome of the SAE will be documented using the definitions/criteria in Section 9.2.

All serious adverse events are to be reported to the Institutional Review Board (IRB) by the Investigator.

Suspected Unexpected Serious Adverse Reaction (SUSAR)

Unexpected adverse reactions are adverse reactions, the nature, severity, consequences, or frequency of which are not consistent with the anticipated risks described in current relevant information (e.g., investigator's brochure) for the investigational product. The investigator's brochure serves as a primary document to provide safety reference information to determine whether an adverse reaction is expected or unexpected. Prior to submitting the appropriate IND safety report, the Sponsor will ensure that the event meets all three of the definitions for "suspected adverse reaction", "serious", and "unexpected".

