9.9 Discontinuation of Treatment/Study Termination Criteria

If a participant in the trial meets criteria for discontinuation and the Investigator is unable to determine whether the adverse event is related to study treatment, the participant should discontinue treatment and be taken off the treatment phase of the study after discussion with the Medical Monitor. The adverse event should be assessed consistent with the Common Terminology Criteria for Adverse Events (CTCAE) v5.0. Unblinding for individual patients may be warranted after consultation with the Medical Monitor for adverse events of CTCAE grade ≥ 3 .

Study treatment should be permanently discontinued for the following:

- The investigator believes that for safety reasons or tolerability reasons (e.g., AE), it is in the best interest of the participant to discontinue study treatment.
- Any Grade 3 non-skin, drug-related AE lasting > 7 days, or recurs with the following exceptions for hypotension (without associated AEs (e.g., dizziness)), diarrhea, or colitis-related symptoms.

The study must be terminated if any of the following criteria are met:

- Two or more study drug-related ≥ Grade 4 AEs or SAEs (unblinding required) of a similar nature that occur in participants that have received SPH3127 and the study team believe that participants would incur undue risk by continuing the study.
- Death (CTCAE grade 5) of any participant in which the cause of death is assessed to be related to study treatment and the participant was found to have received SPH3127.

Study termination requires that no additional participants will be administered study treatment. Participants who have already received study treatment will continue to be followed for safety through the remainder of the planned follow-up period.

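### Section 9.2 rates drug and procedure causality as one item, but the relatedness summary, the SAE assessment and the drug-related rules need attribution to study drug alone

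*Combined protocol and SAP*

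**What the plan says.** Section 9.2 is the only place in the protocol that defines causality categories. It asks for the event's "relationship to the study drug or treatment procedure" and offers Definite, Possible, Unlikely and Not Related. Each of the four definitions is expressed in relation "to the treatment or procedure". There is no second item, and the protocol does not say what counts as a treatment procedure.

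The sections that use the rating ask something narrower:

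- Section 9.1 wants "The Investigator's opinion of the association of each AE to study drug", and adds that "All AEs will be summarized by relatedness to IP".
- Section 9.8 wants "The Investigator's opinion of the relationship of the SAE to study drug", which, with the other SAE attributes, "will be documented using the definitions/criteria in Section 9.2".
- Section 9.9 acts on drug-related events. One study termination criterion begins "Two or more study drug-related ≥ Grade 4 AEs or SAEs (unblinding required) of a similar nature".

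Several procedures take place on treatment. The Schedule of Assessments (4.2) puts a sigmoidoscopy within 2 days after Day 56, and another within 2 days after Day 336 for those in the optional extension. Tissue is taken at each (7.15). Preparation may include a laxative and an enema, and "During the exam, patients may be sedated" (7.14). Serial blood draws take place on Days 1, 28 and 56 (7.16, 7.17).

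**The concern.** The definitions and their use do not match. A joint scale answers whether the tablet or a procedure caused the event; the relatedness summary and the 9.9 rules need to know whether the tablet did. Once a joint rating of Definite or Possible is on file, it does not show which cause the investigator had in mind.

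Safety and tolerability is the primary objective (2.1), so the relatedness summary is one of the tables on which the trial will be read. The overlap also matters for this drug: Section 1.3.1 lists hypotension and dizziness among the events seen with SPH3127 and links them to its mechanism. Both could plausibly also arise around sedation, bowel preparation or repeated blood sampling. This is where drug and procedure opinions most need to be kept apart.

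**Working it through.** The protocol gives no figure to reproduce here, so the main check sets the sections side by side.

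**1. What each section asks and how it is used**

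| Section | Attribution asked for | Use |
|---|---|---|
| 9.2 | Study drug or treatment procedure, jointly | The only category definitions |
| 9.1 | Study drug | Summary of all AEs by relatedness to IP |
| 9.8 | Study drug, on the 9.2 definitions | SAE assessment |
| 9.9 | Drug, study drug or study treatment | Individual discontinuation and study termination |

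Section 9.8 contains the conflict within itself: its question concerns the drug, but the definitions it adopts are joint.

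**2. One event under two readings.** Take a bleed after the Day 56 biopsy that the investigator believes is due wholly to the biopsy.

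- Reading 9.2 literally, and taking a biopsy to be a treatment procedure, the event is clearly related to one of the two named causes. Not Related would be false; Definite fits.
- Answering the 9.1 or 9.8 question, the event is Not Related to study drug.

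The same opinion can therefore land at opposite ends of the scale.

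**3. How much on-treatment exposure to procedures there is.** Section 9.1 counts events as treatment-emergent from first dose to 7 days after last dose. The Day 56 sigmoidoscopy falls in that window for up to 30 patients; the Day 336 one applies only to those who enter and reach the end of the extension. The screening sigmoidoscopy precedes dosing and is left out. Blood is drawn for PK at 7 nominal times per day; the 5 biomarker times are all among them, so there are 7 distinct times per day. Over three days that is 7 × 3 = 21, of which one (Day 1 pre-dose) comes before first dose, leaving 20 per patient.

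**4. Effect on the relatedness summary.** With 10 patients per arm (4.1), one patient whose only related event is a procedure event shifts that arm by 1/10 = 10 percentage points, and the pooled SPH3127 group by 1/20 = 5 points. About 20 sites are planned for 30 patients (5.2, 5.1), or 30/20 = 1.5 patients per site, so differences between sites in how they read 9.2 could not be adjusted for.

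**5. Effect on the termination rule, for scale only.** The protocol gives no rate for serious procedure events, so the per-patient probability p is an assumption. If every such event were read as drug-related, the chance of at least 2 among the 20 patients randomised to SPH3127 is 1 − (1 − p)^20 − 20p(1 − p)^19:

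| Assumed p | Chance of at least 2 in 20 |
|---|---|
| 0.1% | 0.02% |
| 0.5% | 0.4% |
| 1% | 1.7% |
| 2% | 6.0% |
| 5% | 26.4% |

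For the main study these are upper bounds at each assumed rate, because the rule also requires events of a similar kind and a study-team judgement that continuing would put participants at undue risk.

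**The case against.** The strongest reply is that 9.1 and 9.8 already state the question, and it concerns study drug; 9.2 merely supplies category labels. An investigator asked about the drug can rate a biopsy bleed Not Related. Applying the undefined term to sigmoidoscopy, sedation, bowel preparation or venepuncture is an inference. The AE and SAE forms are not among the documents and may already hold two fields.

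All of this is fair. A reader might infer that sites are obliged to record procedure events as Definite; the documents do not support that, because 9.1 and 9.8 point the other way. What remains is that both readings are open, that the inference about procedures is a natural one, and that 9.8 sends sites to the joint wording by section number.

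Two further inferences also go too far:

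- *That two procedure complications would end the study.* The criterion requires study drug-related events of a similar nature in participants who received SPH3127, requires unblinding, and depends on the undue-risk judgement. Separately, before an IND safety report, 9.8 has the sponsor confirm that an event is a suspected adverse reaction.
- *That the joint rating would hide a drug signal such as hypotension.* Sections 10.3 and 10.3.1 summarise TEAEs by treatment group without a causality filter, and 10.3.4 summarises blood pressure and pulse at each scheduled time point. An imbalance would still show there.

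It can also be said that procedures are common to all arms, so any inflation is shared. That holds on average; with 10 patients per arm, one stray rating is still enough to separate two arms by 10 points.

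**Conclusion.** The point holds as an inconsistency that creates a risk of misclassification, not as a certainty of it. Section 9.2 merges two attributions that 9.1, 9.8 and 9.9 need kept apart, and the protocol text gives no means of separating them once data are collected.

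The effect falls on the relatedness summary: 10 percentage points in an arm for each patient whose only related event is a procedure event. The unfiltered TEAE and vital-sign summaries are unaffected, and termination through procedure events alone is unlikely.

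This rests on two assumptions: that some sites would take study procedures to be treatment procedures, and that the AE and SAE forms follow the 9.2 wording. The protocol also does not say which categories count as related. That is a separate gap, and this conclusion does not depend on it.

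**What to change.** In Section 9.2 and on the AE and SAE forms, replace the joint rating with two items on the existing four-level scale:

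1. relationship to study drug;
2. relationship to a study procedure, with the procedures named (sigmoidoscopy, biopsy, sedation, bowel preparation, blood draw).

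State that the 9.1 relatedness summary, the 9.8 assessment and the existing drug-related wording in 9.9 use item 1 only. The clinical criteria in 9.9 stay as they are.

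The cost is one extra field per AE and a few sentences of protocol text. If the CRF already separates the items, only the protocol text needs aligning. The change should be made before events are collected, because a joint rating cannot be reliably split afterwards.

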9.3 Clinical Laboratory Changes

Clinically significant abnormal laboratory test results may, in the opinion of the Investigator, constitute or be associated with an adverse event. Examples of these include abnormal laboratory results that are associated with symptoms or require treatment. Whenever possible, the underlying diagnosis should be listed in lieu of abnormal laboratory values. Laboratory abnormalities deemed not clinically significant (NCS) by the Investigator should not be reported as AEs. Similarly, laboratory abnormalities reported as AEs by the Investigator should not be deemed NCS on the laboratory sheet.

All clinically significant abnormal laboratory test results will be repeated until they return to within normal limits or are at levels that are regarded as clinically non-significant by the Investigator.

9.4 Pregnancy

Pregnancy is neither an AE nor an SAE. However, all pregnancies occurring in subjects or their partner will be followed to assess for pregnancy-associated AEs or SAEs such as congenital anomaly. If, at any time between the first study drug dispensing and 7 days after the last dose of study drug, a pregnancy is suspected, the patient/partner will be instructed/requested to return to the study center within 48 hours and undergo a serum

pregnancy test, as confirmation of pregnancy. All confirmed pregnancies must be immediately reported using the appropriate form.

Upon confirmation of a subject pregnancy, no further investigational treatment will be administered. All pregnancies with study drug exposure will be followed until resolution (i.e., termination [voluntary or spontaneous] or birth).

9.5 Adverse Event Follow-up

For this study, the Investigator will follow AEs until the last day of study participation or up to 7 days thereafter, until the adverse event is resolved or the Investigator determines that the subject is stable, whichever is earlier. Appropriate action may be taken if judged clinically necessary. All AEs identified on the last scheduled contact must be recorded on the AE Case Report Form (CRF) and/or electronic record and the current status (ongoing or resolved) will be noted. In addition, SAEs will be reported to the Sponsor according to the reporting outlines identified in Section 9.8.

9.6 Serious Adverse Event

9.7 Definition of Serious Adverse Event

A SAE is any event that meets any of the following criteria:

- Death
- Life-threatening
- Inpatient hospitalization or prolongation of existing hospitalization
- Persistent or significant disability/incapacity
- Congenital anomaly/birth defect in the offspring of a subject who received SPH3127
- Other: Important medical events that may not result in death, be life-threatening, or require hospitalization, may be considered an SAE when, based upon appropriate medical judgment, they may jeopardize the subject and may require medical or surgical intervention to prevent one of the outcomes listed in this definition. Examples of such events are:
 - Intensive treatment in an emergency room or at home for allergic bronchospasm
 - Blood dyscrasias or convulsions that do not result in inpatient hospitalization
 - Development of drug dependency or drug abuse.

Definition of Terms

Life threatening: An AE is life threatening if the subject was at immediate risk of death from the event as it occurred; i.e., it does not include a reaction that if it had occurred in a more serious form might have caused death. For example, drug-induced hepatitis that resolved without evidence of hepatic failure would not be considered life threatening even though drug-induced hepatitis can be fatal.

Hospitalization: AEs requiring hospitalization should be considered SAEs. Hospitalization for elective surgery or routine clinical procedures that are not the result of an AE (e.g., elective surgery for a pre-existing condition that has not worsened) need not be considered AEs or SAEs. If anything untoward is reported during the procedure, that occurrence must be reported as an AE, either 'serious' or 'non-serious' according to the usual criteria.

In general, hospitalization signifies that the subject has been detained (usually involving at least an overnight stay) at the hospital or emergency ward for observation and/or treatment that would not have been appropriate in the physician's office or outpatient setting. When in doubt as to whether 'hospitalization' occurred or was necessary, the AE should be considered serious.

Disability/incapacitating: An AE is incapacitating or disabling if the experience results in a substantial and/or permanent disruption of the subject's ability to carry out normal life functions.

9.8 Reporting Serious Adverse Events

The recording of SAEs (regardless of their relationship to study drug) will begin with the Screening visit until the Final Visit (Day 56 or 336 (if entering the extension) or Early Termination Visit. Any SAE, including death due to any cause, which occurs during the conduct of this study, regardless of relationship to study drug, must be reported within 24 hours of the Investigator's (or designee's) first awareness of the event.

An initial Serious Adverse Event Form (SAE form) should be completed and submitted through the CRF (or paper form as a backup) per the SAE form instructions.

The Investigators should attempt to group signs and symptoms into a single term that constitutes a single unifying diagnosis and indicated the serious criteria that are applicable to the SAE (the list of serious criteria is also provided in the above section. The Investigator's opinion of the relationship of the SAE to study drug, the duration, intensity, frequency, actions taken with study drug, and the outcome of the SAE will be documented using the definitions/criteria in Section 9.2.

All serious adverse events are to be reported to the Institutional Review Board (IRB) by the Investigator.

Suspected Unexpected Serious Adverse Reaction (SUSAR)

Unexpected adverse reactions are adverse reactions, the nature, severity, consequences, or frequency of which are not consistent with the anticipated risks described in current relevant information (e.g., investigator's brochure) for the investigational product. The investigator's brochure serves as a primary document to provide safety reference information to determine whether an adverse reaction is expected or unexpected. Prior to submitting the appropriate IND safety report, the Sponsor will ensure that the event meets all three of the definitions for "suspected adverse reaction", "serious", and "unexpected".

